### 6.1 Efficacy Analyses

All efficacy analyses will be performed using the FAS, unless otherwise specified.

Tests of significance of BMS-986165 6 mg QD vs. placebo for the coprimary endpoints will be two-sided with a significance level of 0.05. Both coprimary endpoints need to demonstrate statistical significance to result in a successful study.

The key secondary endpoints will be tested with a two-sided significance level of 0.025 to compare BMS-986165 6mg QD vs. placebo and vs. apremilast. A hierarchical testing approach will be used for testing of

Sponsor: Bristol-Myers Squibb

Protocol no: IM011046

key secondary endpoints (see [Section 6.1.3](#)). Two-sided 95% confidence intervals (CIs) will be provided for all efficacy estimates. [REDACTED]

Coprimary and key secondary efficacy endpoints will be displayed graphically by treatment group and visit, as applicable. All efficacy endpoints will be summarized descriptively.

Due to small sample sizes in China and Japan and differences in stratification factors, analyses will be stratified by a combination of the stratification factors used in randomization. The stratified levels are provided below:

- US/PRIOR USE/< 90 KG
- US/PRIOR USE/≥90 KG
- US/NAÏVE/<90 KG
- US/NAÏVE/≥90 KG
- ROW/PRIOR USE/< 90 KG
- ROW/PRIOR USE/≥90 KG
- ROW/NAÏVE/<90 KG
- ROW/NAÏVE/≥90 KG
- JAPAN/PRIOR USE
- JAPAN/NAÏVE
- CHINA/PRIOR USE
- CHINA/NAÏVE

If there is not at least one subject per treatment group in each of the China and Japan strata, then these regions will be collapsed together to form the following stratified levels for analyses:

- US/PRIOR USE/< 90 KG
- US/PRIOR USE/≥90 KG
- US/NAÏVE/<90 KG
- US/NAÏVE/≥90 KG
- ROW/PRIOR USE/< 90 KG
- ROW/PRIOR USE/≥90 KG
- ROW/NAÏVE/<90 KG
- ROW/NAÏVE/≥90 KG
- ASIA/PRIOR USE
- ASIA/NAÏVE

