#### Testing Strategy for Efficacy Endpoints

The primary family of coprimary endpoints will each be tested at a Type I error=0.05 first, and if significant for both endpoints, testing will proceed for the secondary family of key secondary endpoints [REDACTED]. The primary family of coprimary endpoints will be the serial gatekeeper for proceeding with testing of the secondary family of key secondary efficacy endpoints.

Primary Family – Coprimary endpoints compared with placebo; both must be significant at a Type I error=0.05 in order to proceed with the secondary family tests for the key secondary endpoints:

[figure not shown]
- Primary 1: Proportion of subjects who achieve sPGA 0/1 at Week 16
- Primary 2: Proportion of subjects who achieve PASI 75 at Week 16

In order to control for Type I error rate inflation within the secondary family of key secondary endpoints, separate testing branches with a 2-sided Type I error=0.025 will be used for comparisons of BMS-986165 6 mg QD compared to placebo and BMS-986165 6 mg QD compared to apremilast. A hierarchical testing method within each testing branch will be implemented for the key secondary endpoints. The hierarchical test may only proceed to the next key secondary endpoint within each testing branch if the null hypothesis is rejected a Type I error=0.025. If an endpoint fails at any step, then all subsequent p-values will be considered descriptive.

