## 6.1.2 Key Secondary Endpoints

### 6.1.2.1 Binary Endpoints

#### Analysis Model

CMH tests will be used to compare response rates between either BMS-986165 6mg QD and placebo or apremilast using the stratification factors from IRT specified in [Section 6.1](#). The odds ratio (ratio of odds in BMS-986165 6 mg QD group to the odds in the placebo or apremilast group) and the corresponding 2-sided 95% CIs and p-values will be reported. Additionally, treatment differences in proportions and the 95% CI for the treatment difference will be provided.

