### 6.1.2.2 Continuous Endpoints

#### Analysis Model

Analysis of covariance (ANCOVA) models will be used to compare the change between BMS-986165 6 mg QD and placebo or between BMS-986165 6 mg QD and apremilast at Week 16. Treatment group will be included in the model as well as the stratification factors from IRT specified in [Section 6.1](#) and will be considered as fixed effects. The baseline value will be added into the model as a covariate. The adjusted least-squares (LS) means as well as the treatment differences based on LS means and the corresponding 2-sided 95% CIs will be provided for the difference between BMS-986165 6 mg QD and placebo or apremilast.

[figure not shown]

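### Key secondary endpoints are tested at two-sided 0.025 but reported with 95% intervals, so an endpoint that fails its test can carry an interval that excludes no effect.

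*SAP*

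**What the plan says.** **Test level.** The protocol synopsis, under the testing strategy, says that "separate testing branches with a 2-sided Type I error=0.025 will be used" for the placebo and apremilast comparisons. Within a branch the endpoints are tested in order, and p-values after a failed step become descriptive. SAP 6.1 agrees: "The key secondary endpoints will be tested with a two-sided significance level of 0.025".

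**Interval level.** The same paragraph of SAP 6.1 sets a general rule: "Two-sided 95% confidence intervals (CIs) will be provided for all efficacy estimates". The sections on the key secondary endpoints repeat it:

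- SAP 6.1.2.1, odds ratios: "the corresponding 2-sided 95% CIs and p-values will be reported".
- SAP 6.1.2.1, risk differences: "treatment differences in proportions and the 95% CI for the treatment difference will be provided".
- SAP 6.1.2.2, LS-mean differences: "the corresponding 2-sided 95% CIs will be provided for the difference between BMS-986165 6 mg QD and placebo or apremilast".

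Protocol 9.4.2 also uses 95% for the secondary endpoints.

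**Coprimary endpoints.** SAP 6.1 states: "Tests of significance of BMS-986165 6 mg QD vs. placebo for the coprimary endpoints will be two-sided with a significance level of 0.05". Their intervals are 95% as well.

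The text is blacked out directly after the general rule in SAP 6.1. Section 6.1.3, which holds the hierarchy tables, is not visible in the public copy.

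**The concern.** The interval printed beside a test result should lead the reader to the same conclusion as the test, unless the plan says otherwise. Here the test uses 0.025 and the interval corresponds to 0.05, and the visible text neither notes the difference nor gives the intervals a separate descriptive status.

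The mismatch matters most at the step where a branch stops. If the first endpoint to fail has p between 0.025 and 0.05, the report will show an endpoint declared not significant next to an odds ratio whose interval excludes 1, or a difference whose interval excludes 0. A reader of the report, a label or a publication could take that interval as evidence of success. The plan should settle in advance how such an interval is to be read.

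**Working it through.** **Inputs.** Two-sided alpha is 0.025 per key secondary branch and 0.05 for the coprimary endpoints (protocol synopsis; SAP 6.1). The interval level is 95% throughout (SAP 6.1, 6.1.2.1, 6.1.2.2). About 600 subjects are randomized 2:1:1 (protocol 4.2), so about 300/150/150; this is used only for the illustration. No power for the key secondary endpoints is visible, so the powers below are assumptions.

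**1. The plan's own split.** 0.025 + 0.025 = 0.05, so the two branches share two-sided 0.05 equally. This reproduces exactly.

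**2. Multipliers.** A 95% interval uses z(0.975) = 1.9600. A two-sided 0.025 test uses z(0.9875) = 2.2414. The matching interval level is 1 − 0.025 = 97.5%. Width ratio: 2.2414 / 1.9600 = 1.144, so 14.4% wider.

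**3. The gap.** Test and interval disagree when 1.9600 < |z| < 2.2414, that is, when 0.025 < p < 0.05. The disagreement runs one way: an endpoint that passes at 0.025 also has a 95% interval excluding no effect, apart from small differences in method.

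**4. Chance of landing in the gap, for one tested endpoint.** With no true effect it is 0.05 − 0.025 = 2.5%. With a true effect giving a stated power at 0.025, put θ = 2.2414 + z(power). Then, by normal approximation, gap = Φ(2.2414 − θ) − Φ(1.9600 − θ) = (1 − power) − Φ(1.9600 − θ).

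| Assumed power at 0.025 | θ | 1 − power | Φ(1.9600 − θ) | Gap |
|---|---|---|---|---|
| 90% | 3.523 | 0.100 | 0.059 | 4.1% |
| 80% | 3.083 | 0.200 | 0.131 | 6.9% |
| 70% | 2.766 | 0.300 | 0.210 | 9.0% |
| 50% | 2.241 | 0.500 | 0.389 | 11.1% |

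At 95% power the gap is 2.3%.

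**5. Illustration with assumed counts.** Take 87/300 (29.0%) against 30/150 (20.0%), unstratified.

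- Difference: 9.0 points.
- Test: pooled rate 117/450 = 0.26; SE = √(0.26 × 0.74 × (1/300 + 1/150)) = 0.0439; z = 2.05; p = 0.040. This fails at 0.025.
- Interval SE = √(0.29 × 0.71/300 + 0.20 × 0.80/150) = 0.0419.
- 95% interval: 9.0 ± 1.960 × 4.19, or 0.8 to 17.2 points. It excludes 0.
- 97.5% interval: 9.0 ± 2.241 × 4.19, or −0.4 to 18.4 points. It includes 0.

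**6. A limit of the match.** The agreement is close but not exact when test and interval use different variances. With 89/300 against 30/150, p = 0.028 fails, yet the 97.5% interval (0.3 to 19.1 points) still just excludes 0. A 97.5% interval narrows the region of conflict; it does not remove it.

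**The case against.** The strongest reply is that nothing inferential is broken. The decision rule is stated clearly, no visible text uses an interval to declare success, and giving 95% intervals for estimation beside an alpha-adjusted test is a common reporting choice. This stands, and it limits the point to reporting and interpretation.

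Four stronger readings are tempting, and the documents do not support them:

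- **That type I error is inflated or false claims follow.** Rejection depends on the 0.025 test alone. The mismatch affects only an endpoint already declared a failure.
- **That every interval in the plan is at the wrong level.** The coprimary intervals match their 0.05 tests and need no change.
- **That the per-endpoint chances add up.** The SAP lists 13 apremilast comparisons (7 at Week 16, 3 at Week 24, 3 for Weeks 24 and 52 together) and 6 or 7 placebo comparisons. The conflict at a stopping step can occur at most once per branch and requires every earlier endpoint in that branch to have passed. The percentages are not conditioned on this, and the endpoints are correlated, so summing them would be wrong.
- **That 97.5% intervals would make the intervals multiplicity-adjusted.** One interval from each branch would have joint coverage of at least 95% at the 97.5% level, against 90% at the 95% level. That bound does not extend across all endpoints in the hierarchy. Endpoints after a failed step can have intervals excluding no effect at either level and still be only descriptive.

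The redaction also counts. A caveat or a companion interval may sit in the blacked-out text of SAP 6.1 or in 6.1.3, so it cannot be said that the plan lacks one. The visible 95% wording in 6.1.2.1 and 6.1.2.2 remains, so those intervals will be reported in any case.

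**Conclusion.** The mismatch is real in the visible text and agrees between protocol and SAP. It is a modest reporting problem that is cheap to correct. Its size is the range 0.025 < p < 0.05: 2.5% per tested endpoint under no effect, and about 4% to 11% for powers from 90% down to 50%. Those powers are assumptions and the calculation is a normal approximation; higher power gives a smaller figure. The conclusion rests on the visible wording and would soften to a matter of cross-reference if the redacted text already labels the 95% intervals as nominal or adds a 97.5% interval.

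**What to change.** In SAP 6.1, 6.1.2.1 and 6.1.2.2:

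- Report two-sided 97.5% intervals for the key secondary odds ratios, risk differences and LS-mean differences.
- Keep the 95% intervals for these comparisons if wanted, labelled as nominal and not adjusted for multiplicity.
- State that significance follows only from the hierarchical test, so that intervals for endpoints after a failed step are descriptive at either level. This sentence is needed even with 97.5% intervals.
- Leave the coprimary 95% intervals as they are.

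If the redacted text already says this, a cross-reference from 6.1.2.1 and 6.1.2.2 is enough. The cost is a few sentences and one programming option, with key secondary intervals 14% wider. No test, sample size or data collection changes.

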#### **4.1.2 Treatment Period**

Qualified subjects who have completed the screening procedures and have met the inclusion/exclusion criteria will be randomized on Day 1 in a 2:1:1 ratio, respectively to one of the following 3 treatment groups:

- BMS-986165 6 mg QD
- Placebo
- Apremilast titrated to 30 mg BID as follows:
  - Day 1: 10 mg tablet in the morning
  - Day 2: 10 mg tablet in the morning and evening
  - Day 3: 10 mg tablet in the morning and 20 mg tablet in the evening
  - Day 4: 20 mg tablet in the morning and the evening
  - Day 5: 20 mg tablet in the morning and 30 mg tablet in the evening
  - Day 6 and thereafter: 30 mg tablet in the morning and the evening

Dummy tablets (placebo to the BMS-985165 6 mg tablet, placebo to apremilast 30 mg tablet BID, and placebo to apremilast 10 mg, 20 mg, and 30 mg during titration) will be administered to the subjects to maintain blinding. Additional details are provided in Section 6.1. Note that apremilast will not be used as a treatment arm in China.

Randomization should not occur until at least 8 days after the Screening Visit to allow collection of PSSD data during screening in order to calculate a baseline PSSD score. Randomization will be stratified by geographic region (U.S., Japan [body weight stratum will not be applied in Japan], China [body weight stratum will not be applied in China], and Rest of World), previous biologic use (for psoriasis, psoriatic arthritis or other inflammatory diseases only; yes/no), and body weight ( $\geq 90$  kg and  $< 90$  kg). If subjects from China are not enrolled in the study, then the stratification level for China will not be utilized. As this is designed to be a global study across multiple countries, randomization in each country will be targeted to approximately 35% or less of the total sample size. This change is being implemented to achieve geographical representation across countries and to minimize the potential for any single country to have a disproportionate impact on the overall efficacy and/or safety profile.

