## 5.0 Populations for Analyses

The following analysis sets will be used in the summary and analysis of study data:

- **Enrolled population:** All subjects who sign informed consent.
- **Full Analysis Set (FAS):** All subjects who are randomized. Following the intent-to-treat (ITT) principle, subjects will be analyzed according to the treatment group assigned at randomization. The FAS will be the primary efficacy analysis population.
- **Per Protocol Set (PPS):** A subset of the FAS who are compliant with study treatment and who do not have any relevant protocol deviations that may impact the coprimary efficacy endpoint assessments. The PPS will be analyzed according to the treatment assigned at randomization. The PPS will be a supportive efficacy analysis population and only the co-primary endpoints will be analyzed using this set.
- **As-treated population:** All randomized subjects who take at least one dose of study treatment. Subjects will be analyzed according to treatment received.

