## 6.0 Statistical Analyses

Descriptive summaries and analyses will be presented for data captured throughout the study using the following treatment groups.

During the first 16 weeks of treatment, summaries will be provided for the following treatment groups:

- BMS-986165 6 mg QD
- Apremilast
- Placebo

During the first 24 weeks of treatment, summaries will be provided for the following treatment groups:

- BMS-986165 6 mg QD (subjects continuously taking BMS-986165 6 mg QD)
- Apremilast

Summaries will be provided for subjects who have continuous treatment throughout the entire study with either BMS-986165 or apremilast using the following treatment groups:

- BMS-986165 6 mg QD
- Apremilast

Summaries of all subjects exposed to BMS-986165 6 mg QD will also be provided as applicable. Adverse events will be summarized using exposure-adjusted incidence rates (EAIR) for these summaries.

Please note that there will be no Chinese subjects in the apremilast group due to lack of market approval of the agent in China.

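### If Chinese subjects are enrolled, the China/Japan collapse rule is triggered by design in the apremilast comparison, and part of the ASIA contrast against apremilast is then not randomised

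*SAP*

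**What the plan says.** SAP 6.1 lists 12 analysis strata: eight for the US and Rest of World (region by prior biologic use by weight), two for Japan and two for China. It then gives a fallback, with the trigger "If there is not at least one subject per treatment group in each of the China and Japan strata". When it applies, Japan and China are joined as ASIA/prior use and ASIA/naïve, and the list shrinks to ten levels.

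SAP 6.0 states that "there will be no Chinese subjects in the apremilast group". SAP 2.1 and 2.3 agree, and Protocol 4.1.2 says "Note that apremilast will not be used as a treatment arm in China". Chinese enrolment was itself conditional: "If subjects from China are not enrolled in the study, then the stratification level for China will not be utilized" (Protocol 4.1.2).

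The full analysis set in SAP 5.0 is "All subjects who are randomized. Following the intent-to-treat (ITT) principle", and SAP 6.1 uses it for all efficacy analyses unless otherwise specified. The strata of 6.1 feed both kinds of apremilast comparison. The binary endpoints (6.1.2.1) are covered by the sentence "CMH tests will be used to compare response rates between either BMS-986165 6mg QD and placebo or apremilast", which points to those strata. The ANCOVA (6.1.2.2) takes the same levels as fixed effects: "Treatment group will be included in the model as well as the stratification factors from IRT specified in" the list in 6.1. Key secondary endpoints are tested at a two-sided 0.025.

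**The concern.** A rule for sparse strata should respond to chance emptiness. Here one cell, China by apremilast, is empty by design, so the rule fires whenever China contributes anyone and apremilast is among the groups counted.

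The merge changes what is estimated. Unmerged, a China stratum has no apremilast subjects and contributes nothing to a CMH comparison with apremilast. Merged, Chinese BMS-986165 subjects are set against Japanese apremilast subjects, although they could never have been assigned apremilast. The Japanese part of the contrast is still randomised; the Chinese part is not.

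At stake are the alpha-controlled superiority claims over apremilast at Weeks 16, 24 and 52. If Chinese subjects respond better than Japanese subjects, a false claim becomes more likely. If they respond worse, the test is biased against BMS-986165.

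**Working it through.** **1. Is the trigger met?** Take the best case, with every permitted China and Japan cell well filled and China/apremilast = 0.

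- All three groups counted: met.
- Only BMS-986165 and apremilast counted: met.
- Only BMS-986165 and placebo counted: not automatic.

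For the apremilast comparison, both natural readings (all groups, or the two being compared) lead to the merge. If no Chinese subject is enrolled, the point does not arise.

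**2. What the merged stratum estimates.** With no drug effect, the expected ASIA difference is

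(Chinese share of ASIA BMS-986165 subjects) × (China rate − Japan rate).

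This is zero only if the two rates are equal. The Mantel-Haenszel weight of a stratum is n1·n0/(n1+n0), so

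overall bias = ASIA weight share × Chinese share × gap.

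**3. Inputs.** From the documents: about 600 subjects at 2:1:1, hence 300 BMS-986165 and 150 apremilast, and a two-sided alpha of 0.025 (1.25% per tail). Assumed, because the documents are silent: Japan 20/10 or 40/20 (BMS-986165/apremilast), 10 to 60 Chinese BMS-986165 subjects, 35% response, and a gap of 10 or 20 points in either direction.

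**4. Worked examples (Japan 40/20, 20-point gap).**

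- 20 Chinese subjects: ASIA is 60 vs 20, weight 60×20/80 = 15.0. The rest is 240 vs 130, weight 240×130/370 = 84.3. ASIA share = 15.0/99.3 = 15.1%. Chinese share = 20/60 = 33.3%. Bias = 0.151 × 0.333 × 20 = 1.0 point.
- 60 Chinese subjects: ASIA is 100 vs 20, weight 16.7. The rest is 200 vs 130, weight 78.8. ASIA share = 17.5%. Chinese share = 60%. Bias = 0.175 × 0.60 × 20 = 2.1 points.

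**5. Error rates.** These come from simulating the CMH test with no drug effect (200,000 replicates, eight US/Rest of World strata plus two ASIA strata, 40/60 split on biologic use assumed). The last column is the tail favouring BMS-986165 when China responds better; its nominal value is 1.25%. Paired values are for a 10- and a 20-point gap.

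| Chinese BMS-986165 subjects | Japan | Bias, points | Two-sided error | Favourable tail |
|---|---|---|---|---|
| 10-20 | 20/10 or 40/20 | 0.25-0.5; 0.5-1.0 | 2.5-2.8% (both gaps) | 1.4-2.0% (both gaps) |
| 40-60 | 20/10 | 0.6-0.7; 1.2-1.4 | 2.6-2.7%; 2.9-3.3% | 1.6-1.7%; 2.2-2.4% |
| 40-60 | 40/20 | 0.8-1.05; 1.6-2.1 | 2.6-2.9%; 3.2-4.1% | 1.8-2.0%; 2.7-3.3% |

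If China responds worse, the favourable tail in the first row falls to 0.7-1.0%. With China left unmerged, the two-sided error is 2.4-2.6% throughout.

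**6. ANCOVA.** The same weights apply. With Japan 40/20, a 10-point China-Japan difference in PSSD symptom change (0-100 scale) moves the LS-mean difference by 0.29, 0.50, 0.82 and 1.05 points for 10, 20, 40 and 60 Chinese subjects. A simulation with an assumed residual SD of 22 gave 0.27, 0.47, 0.84 and 1.08, and about zero with China excluded or kept as separate strata.

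**The case against.** **The wording is ambiguous.** SAP 6.1 does not define treatment group. It could mean the groups that exist in each region, or BMS-986165 and placebo only; the merge is then not automatic and China can stay separate. That is fair, but the SAP does not say so, and both natural readings for an apremilast comparison trigger the merge. Even on the narrow reading, one sparse China or Japan cell would cause it and produce the same contrast.

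**Relevant text may be unseen.** Section 6.1.3, a redacted part of 6.1 and the China-specific amendments are not available and might exclude China. This stands as a limit on certainty. If such text exists, 6.1 needs only a cross-reference.

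**The effect is conditional and probably small.** Bias needs Chinese enrolment, Japanese apremilast subjects at the same biologic-use level and a real regional gap. SAP 6.1 itself describes the China and Japan samples as small, which points to the first row of the table. This limits the severity, not the validity.

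**The assumed 300 vs 150 split does not fit the design.** Adding Chinese subjects to BMS-986165 only, within fixed totals, leaves the rest of the trial at 240:130 or 200:130 rather than 2:1. Correct. At 240:120 the ASIA share is 15/95 = 15.8% and the bias 1.05 points. At 200:100 it is 16.7/83.3 = 20% and the bias 0.20 × 0.60 × 20 = 2.4 points. The correction makes the bias slightly larger.

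**Excluding China goes further than needed.** Separate China strata do remove the bias, in the ANCOVA as well. But Chinese subjects would still influence the baseline slope and residual variance there while adding no information on the contrast. Exclusion does mean a different BMS-986165 denominator for the apremilast comparison, which the tables must state.

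**Conclusion.** The rule is wrong as written for the apremilast comparisons: it counts a group that China cannot have, and so brings non-randomised data into confirmatory tests. Pooling sparse strata is not the fault; Protocol 9.4.1 and 9.4.2 allow it.

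The conclusion depends on Chinese subjects being enrolled, on apremilast being counted in the rule, on Japanese apremilast subjects in the same ASIA level, and on no unseen text excluding China. Its size rests entirely on assumed counts and gaps. With few Chinese subjects the distortion is minor (two-sided error at most 2.8%). It becomes material only with many Chinese subjects and a large gap (about 4%; bias about 2 points, or 2.4 at exact 2:1 allocation outside Asia).

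The coprimary comparison is not threatened, because Chinese subjects have a concurrent placebo control. The point should be fixed because it affects alpha-controlled claims and is avoidable at almost no cost.

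**What to change.** In SAP 6.1, state that:

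1. the collapse condition is assessed separately for each comparison, counting only the two groups compared;
2. subjects randomised in China are excluded from every BMS-986165 versus apremilast analysis (CMH, ANCOVA and the response rates shown with them), and China is never merged with Japan for that comparison.

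The two statements are consistent: with China excluded, the check for the apremilast comparison concerns Japan only. If a section not available here already excludes China, a cross-reference in 6.1 is enough.

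The cost is one or two sentences, a filter in the apremilast programs, and a table footnote giving the BMS-986165 denominator for that comparison. No randomised information is lost, because Chinese subjects have no concurrent apremilast control.
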